12.7 Interim Analyses and Reporting

There are no plans to conduct an interim analysis and no criteria by which the study would be terminated early based upon statistical determination.

12.8 Sample Size Justification

Sample size calculation was based on extended wear clinical studies from three PMA studies [REDACTED] and one 52-week extended wear study [REDACTED] that evaluated 5 currently marketed silicone hydrogel contact lenses. The weighted average, based on sample size, on the proportion of ocular serious and significant non-serious ADEs obtained from these five contact lenses was 0.045. Therefore, assuming that the expected difference between test and control is 0 and that the control proportion is 0.045, a sample size of 213 per group will provide 80% power to reject the null hypothesis of inferiority in test compared to control, with a noninferiority margin of 0.05 (5%).

Taking into consideration the exposure duration of 12 months, approximately 568 subjects will be randomized (284 test and 284 control) to compensate for approximately 25% drop-out rate.

13 DATA HANDLING AND ADMINISTRATIVE REQUIREMENTS

13.1 Subject Confidentiality

The Investigator must ensure that the subject's anonymity is maintained throughout the course of the study. In particular, the Investigator must keep an enrollment log with

confidential identifying information that corresponds to the subject numbers and initials of each study participant. At the end of the clinical study, the Study Sponsor will collect a copy of the enrollment log *without any identifying subject information*. All documents submitted to the Study Sponsor will identify the subjects exclusively by number and demographic information. No other personally identifying information will be transmitted to the Study Sponsor.

The Study Sponsor may release anonymized study data to external researchers for purposes of future research directly related to the study objectives, or future research that is beyond the scope of the current study objectives. The Informed Consent Form explains this to study subjects. Anonymization means that all identifiable information will be removed from the dataset and all links to the subjects in the study will be removed. Anonymization of the data will maintain confidentiality of the subjects who participate in the study so that they cannot be identified by external researchers. The anonymized data set will contain records from all of the subjects in the current study, but the anonymization process might change the data set in some ways, so external researchers will be informed that they might not be able to duplicate some of the results from this study.

13.2 Completion of Source Documents and Case Report Forms

The nature and location of all source documents will be identified to ensure that original data required to complete the CRFs exist and are accessible for verification by the site monitor, and all discrepancies shall be appropriately documented via the query resolution process. Site monitors are appointed by the Study Sponsor and are independent of study site staff.

If electronic records are maintained, the method of verification must be determined in advance of starting the study.

At a minimum, source documents include the following information for each subject:

- Subject identification (name, sex, race/ethnicity)
- Documentation of subject eligibility
- Date of informed consent
- Dates of visits
- Documentation that protocol specific procedures were performed
- Results of study parameters, as required by the protocol
- IP accountability records

- Documentation of AEs and other safety parameters (if applicable)
- Records regarding medical histories and the use of concomitant therapies prior to and during the study
- Date of study completion and reason for early discontinuation, if applicable

It is required that the author of an entry in the source documents be identifiable. Direct access to source documentation (medical records) must be allowed for the purpose of verifying that the data recorded on the CRF are consistent with the original source data.

Only designated individuals at the site will complete the CRFs. The CRFs must be completed at regular intervals following the clinical study visit schedule. It is expected that all data reported have corresponding entries in the source documents. The Principal Investigator is responsible for reviewing and certifying that the CRFs are accurate and complete. The only subject identifiers recorded on the CRFs will be subject number, and subject demographic information.

13.3 Data Review and Clarifications

A review of CRF data to the subject's source data will be completed by the site monitor to ensure completeness and accuracy. After the CRFs have been completed, additional data clarifications and/or additions may be needed as a result of the data cleaning process. Data clarifications are documented and are part of each subject's CRF.

13.4 Sponsor and Monitoring Responsibilities

The Study Sponsor will designate a monitor to conduct the appropriate site visits at the appropriate intervals according to the study monitoring plan. The clinical investigation will be monitored to ensure that the rights and well-being of the subjects are protected, the reported data are accurate, complete, and verifiable from the source documents, and the study is conducted in compliance with the current approved protocol (and amendments[s], if applicable), with current GCP, and with applicable regulatory requirements.

The site may not screen subjects or perform the informed consent process on any subject until it receives a notification from an appropriate Study Sponsor representative that the site may commence conducting study activities. Monitoring will be conducted periodically while the clinical study is ongoing. Monitoring methods may include site visits, telephone, written and fax correspondence. Close-out visits will take place after the last visit of the last subject at the site.

A Coordinating Investigator may be identified by the Study Sponsor to review and endorse the final study report. In cases where a Coordinating Investigator is engaged, the Study Sponsor will select the Coordinating Investigator based upon their experience, qualifications, active study participation, and their willingness and availability to take on this role.

13.5 Regulatory Documentation and Records Retention

The Investigator is required to maintain up-to-date, complete regulatory documentation as indicated by the Study Sponsor and the Investigator's files will be reviewed as part of the ongoing study monitoring. Financial information is to be kept separately.

Additionally, the Investigator must keep study records and source documents consistent with the terms of the clinical study agreement with the Study Sponsor. If the Investigator retires, relocates, or for any other reason withdraws from responsibility of keeping the study records, then the Study Sponsor must be notified and suitable arrangements made for retention of study records and source documents needed to comply with national and international regulations.

13.6 Quality Assurance and Quality Control

The Study Sponsor will secure agreement from all involved parties to ensure direct access to all study related sites, source data and documents, and reports for the purpose of monitoring and auditing by the Study Sponsor, and inspection by domestic and foreign regulatory authorities. Quality control will be applied to each stage of data handling to ensure that all data are reliable and have been processed correctly. Agreements made by the Study Sponsor with the Investigator/Institution and any other parties involved in the clinical study will be provided in writing as part of the protocol or as a separate agreement.

14 ETHICS

This clinical study must be conducted in accordance with the ethical principles contained within:

- The Declaration of Helsinki, and in compliance with the ICH E6 GCP Consolidated Guideline, ISO 14155:2011, and the applicable US FDA 21 CFR Regulations.
- SOPs of the Study Sponsor and contract research organizations participating in the conduct of the clinical study and all other applicable regulations.
- Notifications and timelines for reporting protocol deviations should be based upon applicable Ethics Committee requirements

The Investigator must ensure that all personnel involved in the conduct of the study are qualified to perform their assigned responsibilities through relevant education, training, and experience. The Investigator and all clinical study staff must conduct the clinical study in compliance with the protocol. Deviations from this protocol, regulatory requirements, and/or GCP must be recorded and reported to the Sponsor prior to database lock. If needed, corrective and preventive action should be identified, implemented, and documented within the study records. Use of waivers to deviate from the clinical protocol is prohibited.

Before clinical study initiation, this protocol, the informed consent form, any other written information given to subjects, and any advertisements planned for subject recruitment must be approved by an IRB/IEC. The Investigator must provide documentation of the IRB/IEC approval to the Study Sponsor. The approval must be dated and must identify the applicable protocol, amendments (if any), informed consent form, assent form (if any), all applicable recruiting materials, written information for subject, and subject compensation programs. Any Investigator who practices and intends to see study subjects at a hospital or university may require secondary review and approval by an IRB belonging to that institution. A copy of local or secondary IRB approvals should be provided to the Study Sponsor. The IRB/IEC must be provided with a copy of the IB, any periodic safety updates, and all other information as required by local regulation and/or the IRB/IEC. At the end of the study, the Investigator must notify the IRB/IEC about the study's completion. The IRB/IEC also must be notified if the study is terminated prematurely. Finally, the Investigator must report to the IRB/IEC on the progress of the study at intervals stipulated by the IRB/IEC.

Voluntary informed consent must be obtained in writing from every subject and the process shall be documented before any procedure specific to the clinical investigation is applied to the subject. The Investigator must have a defined process for obtaining consent. Specifically, the Investigator, or their delegate, must explain the clinical study to each potential subject and the subject must indicate voluntary consent by signing and dating the approved informed consent form. The subject must be provided an opportunity to ask questions of the Investigator, and if required by local regulation, other qualified personnel. The Investigator must provide the subject with a copy of the consent form written in a language the subject understands. The consent document must meet all applicable local laws and provide subjects with information regarding the purpose, procedures, requirements, and restrictions of the study, along with any known risks and potential benefits associated with the IP and the study, the available compensation, and the established provisions for maintaining confidentiality of personal, protected health information. Subjects will be told about the voluntary nature of participation in the study and must be provided with contact information for the appropriate individuals should questions or concerns arise during the study. The subject also must be told

that their records may be accessed by appropriate authorities and Sponsor-designated personnel. The Investigator must keep the original, signed copy of the consent (file in subject's medical records) and must provide a duplicate copy to each subject according to local regulations.

Short Title:

**Statistical Analysis Plan
CLL949-C010**

Full Title:

**Statistical Analysis Plan - US
CLL949-C010 / NCT04085328**

Protocol Title: Clinical Safety and Effectiveness Assessment of an
Investigational Frequent Replacement Silicone Hydrogel Lens

[REDACTED]

[REDACTED]

Reference Number:

Protocol TDOC Number: TDOC-0055758

[REDACTED]

[REDACTED]

[REDACTED]

Approvals:

See last page for electronic approvals.

Job Notes:

This is the fourth revision (Version 5.0) of the Statistical Analysis Plan for this study. This version of the Statistical Analysis Plan is based on Version 5.0 of the study protocol.

Executive Summary:

Key Objectives:

The objective of this study is to demonstrate safety and effectiveness of [REDACTED] soft contact lenses as compared to BIOFINITY® (Biofinity) soft contact lenses, when both study lenses are worn for extended wear (6 nights/7 days of continuous wear followed by 1 night of no lens wear) and replaced on a weekly basis.

Decision Criteria for Study Success:

Success of this study will be based on demonstration of noninferiority in proportion of ocular serious and significant non-serious adverse device effects (ADEs) with [REDACTED] soft contact lenses when compared to Biofinity soft contact lenses, using a margin of 0.05.

Table of Contents

Statistical Analysis Plan - US CLL949-C010	1
Table of Contents	3
List of Tables.....	4
1 Study Objectives and Design.....	5
1.1 Study Objectives.....	5
1.2 Study Description	5
1.3 Randomization.....	6
1.4 Masking	7
1.5 Interim Analysis.....	7
2 Analysis Sets.....	7
2.1 All Enrolled	7
2.2 Enrolled Dispensed.....	7
2.3 Enrolled Not Dispensed.....	7
2.4 Completed.....	7
2.5 Discontinued.....	8
3 Subject Characteristics and Study Conduct Summaries	8
4 Effectiveness Analysis Strategy.....	8
4.1 Effectiveness Endpoints	9
4.2 Effectiveness Hypotheses	9
4.3 Statistical Methods for Effectiveness Analyses.....	10
4.3.1 Primary Effectiveness Analyses	10
[REDACTED]	
[REDACTED]	
[REDACTED]	
4.6 Interim Analysis for Effectiveness	11
5 Safety Analysis Strategy	11
5.1 Safety Endpoints.....	11
5.2 Safety Hypotheses	12
5.3 Statistical Methods for Safety Analyses	12
5.3.1 Primary Safety Analysis	12

5.3.2	Other Safety Analysis	13
5.3.2.1	Adverse Events	13
5.3.3	Biomicroscopy Findings/Slit Lamp Examination	14
5.3.4	Device Deficiencies.....	14
7	Sample Size and Power Calculations	15
10	Revision History	17
11	Appendix.....	25

List of Tables

Table 1-1 Study Description Summary	5
Table 7-1 Historical Extended Wear Study AE Rates	15
Table 8-1 Analysis Windows	16
Table 11-1 Schedule of Study Procedures and Assessments ^a	25

1 Study Objectives and Design

[REDACTED]
[REDACTED].

[REDACTED] this statistical analysis plan describes the analytical strategy to be undertaken to evaluate the Primary cohort [REDACTED]

[REDACTED]

1.1 Study Objectives

PRIMARY OBJECTIVE

The objective of this study is to demonstrate safety and effectiveness of [REDACTED] soft contact lenses as compared to Biofinity soft contact lenses, when both study lenses are worn for extended wear (6 nights/7 days of continuous wear followed by 1 night of no lens wear) and replaced on a weekly basis.

1.2 Study Description

Key components of the study are summarized in Table 1-1.

Table 1-1 Study Description Summary

Study Design	Prospective, multi-center, randomized, [REDACTED] controlled, double-masked, parallel-group
Study Population	
Volunteer subjects aged 18 or over who are adapted daily wear or extended wear frequent replacement soft contact lens wearers, have at least 3 months of soft contact lens wearing experience, and who wear their habitual lenses at least 5 days per week.
 
Subjects must have regularly worn their habitual lenses for at least 10 hours per day. Additionally, extended wear lens wearers must have regularly worn their habitual lenses for at least 1 night per week. Subjects must require contact lens correction in the power range available for this study as specified in the inclusion criteria.
 
[REDACTED] [REDACTED] [REDACTED] [REDACTED]
 
[REDACTED] Pregnant and breastfeeding women are excluded from this study.

	
Primary Cohort [REDACTED]
 
o Completed: minimum 213 completed each in test and controlo Planned: ~632 enrolled, and ~568 randomized (~284 each in test and control) 
[REDACTED]
 
[REDACTED]
 
[REDACTED]

Number of Sites	~45 (US) [REDACTED]
Test Product	soft contact lenses [REDACTED]
Control Product	CooperVision® BIOFINITY® (comfilcon A) soft contact lenses (Biofinity)
Duration of Treatment	Approximately 12 months
Visits	
Visit 1: Baseline/Dispense
 
Visit 2: 24-Hour Follow-Up (24 ± 4 hours)
 
Visit 3: 1-Week Follow-Up (7 ± 2 days)
 
Visit 4: 1-Month Follow-Up (30 ± 4 days)
 
Visit 5: 2-Month Follow-Up (60 ± 7 days)
 
Visit 6: 3-Month Follow-Up (90 ± 7 days)
 
Visit 7: 6-Month Follow-Up ($189 -7/+14$ days)
 
Visit 8: 9-Month Follow-Up (270 ± 14 days)
 
Visit 9: 12-Month Follow-Up/Exit (365 ± 14 days)

1.3 Randomization

A member of the Randomization Programming group at Alcon who is not part of the study team will generate the randomized allocation schedule(s) for study lens assignment. Randomization will be implemented in the Electronic Data Capture (EDC)/Interactive Response Technology (IRT) integration system.

Subjects will be randomized in a 1:1 ratio to receive either [REDACTED] or Biofinity contact lenses, respectively. [REDACTED]

[REDACTED]

[REDACTED]

[REDACTED]

Randomization schedule will be blocked to ensure a balance (1:1) in lens allocation within sites.

1.4 Masking

This study is double-masked.

1.5 Interim Analysis

There are no plans to conduct an interim analysis and no criteria by which the study would be terminated early based upon statistical determination.

2 Analysis Sets

2.1 All Enrolled

All subjects who have signed the informed consent for the study will be included in the All Enrolled analysis set.

2.2 Enrolled Dispensed

Enrolled Dispensed is a subset of All Enrolled subjects/eyes that have been exposed to study lenses.

2.3 Enrolled Not Dispensed

Enrolled Not Dispensed is a subset of All Enrolled subjects/eyes that have not been exposed to study lenses.

2.4 Completed

The Completed analysis set consists of Enrolled Dispensed subjects/eyes completing the study.

2.5 Discontinued

The Discontinued analysis set consists of Enrolled Dispensed subjects/eyes not completing the study.

3 Subject Characteristics and Study Conduct Summaries

Demographic information (age, sex, ethnicity, and race), recent lens wearing experience (wear modality, wear success), and habitual lens information will be presented by lens group and overall for the All Enrolled analysis set.

Baseline data will be summarized by lens group, for Completed and Discontinued analysis sets separately, as applicable.

The following tables and listings for study conduct summaries will be presented:

- Accountability by Eyes Enrolled in the Study and Distribution by Status
- Listing of Lens Assignment by Investigator
- Discontinued Subjects Tabulated by Completed Visits and Reason for Discontinuation with Incidence Rates
- Listing of Subjects Discontinued from Study
- Listing of Out-of-Window Visits

4 Effectiveness Analysis Strategy

This study defines one primary effectiveness endpoint [REDACTED]

[REDACTED] Unless otherwise specified, separate summary tables will be presented for the Completed and the Discontinued analysis sets with the following distinction:

- Completed Control (eyes/subjects)
- Completed Test (eyes/subjects)
- Discontinued Control (eyes/subjects)
- Discontinued Test (eyes/subjects)

No inferential testing will be performed on the effectiveness endpoints, and format of the reporting tables will reference FDA's 510(k) guidance document (Clinical Appendix C, Summary of Reporting Tables; Clinical Appendix D, Trend Analysis Profile) as well as ISO 11980:2012 (Appendix A.3, Reporting of Results).

4.1 Effectiveness Endpoints

Primary Endpoint

The primary endpoint is distance visual acuity (VA) with study lenses, collected in Snellen, for each eye. Conversion will be made to the logMAR scale.

For more information, contact the Office of the Vice President for Research and the Office of the Vice President for Student Affairs.

© 2019 Pearson Education, Inc.

For more information, contact the Office of the Vice President for Research and Economic Development at [contact] or [contact].

[REDACTED]

■ XXXXXXXXXX

[REDACTED]

4.2 Effectiveness Hypotheses

Primary Effectiveness

No inferences are to be made on the primary effectiveness endpoint; therefore, no hypotheses are formulated.

10.1007/s00332-010-9000-0

For more information, contact the Office of the Vice President for Research and Economic Development at [contact] or [contact].

For more information, contact the Office of the Vice President for Research and the Office of the Vice President for Student Affairs.

4.3 Statistical Methods for Effectiveness Analyses

4.3.1 Primary Effectiveness Analyses

Summary statistics will be provided at each visit (Dispense, 24 hours, 1 week, 1 month, 2 months, 3 months, 6 months, 9 months, 12 months, and all unscheduled visits combined). Counts and percentages on the Snellen categories will be displayed, and descriptive statistics (number of observations, mean, standard deviation, median, minimum, and maximum) for the converted logMAR values will be provided.

For more information, contact the Office of the Vice President for Research and Economic Development at [contact] or [contact].

4.6 Interim Analysis for Effectiveness

No interim analysis is planned for effectiveness endpoints.

5 Safety Analysis Strategy

Unless otherwise specified, separate summary tables will be presented for the Completed and the Discontinued analysis sets with the following distinction:

- Completed Control (eyes/subjects)
- Completed Test (eyes/subjects)
- Discontinued Control (eyes/subjects)
- Discontinued Test (eyes/subjects)

Subjects/eyes will be categorized under the actual lens exposed.

5.1 Safety Endpoints

Primary Endpoint

The primary safety endpoint is the proportion of ocular serious and significant non-serious ADEs, calculated as the number of eyes reporting at least one treatment-emergent device-related ocular serious adverse event (AE) or treatment-emergent device-related ocular significant non-serious AE. A binary variable will be defined for each eye as present/absent with the event of interest.

Other Endpoints

Other safety endpoints include the following:

- AEs (non-serious, non-significant)
- Biomicroscopy Findings/Slit Lamp Examination
 - Limbal hyperemia
 - Bulbar hyperemia
 - Corneal staining
 - Conjunctival staining
 - Palpebral conjunctival observations

- Corneal epithelial edema
- Corneal stromal edema
- Corneal vascularization
- Conjunctival compression/indention
- Chemosis
- Corneal infiltrates
- Other findings
- Device deficiencies

5.2 Safety Hypotheses

Primary Safety

The null and alternative hypotheses for the primary analysis are formulated in terms of the predefined margin of 0.05 for noninferiority:

$$H_0: P_T - P_C \geq 0.05$$

$$H_a: P_T - P_C < 0.05$$

where P_T and P_C denote the proportion of eyes reporting ocular serious and significant non-serious ADEs with Mercury and Biofinity contact lenses, respectively.

[figure not shown]
[figure not shown]
Other Safety

No inferences are to be made on other safety endpoints; therefore, no hypotheses are formulated.

5.3 Statistical Methods for Safety Analyses

5.3.1 Primary Safety Analysis

Proportion of events will be analyzed using a generalized linear model, with a logit link function, accounting for within-subject correlation. Site and Site-by-Treatment interaction terms will also be included to assess potential effect of sites on treatment difference. A one-sided 95% upper confidence limit (UCL) will be calculated for the difference in proportions between treatments (Mercury minus Biofinity), and the null hypothesis will be rejected if $UCL < 0.05$.

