8 STUDY POPULATION

The study population consists of adult male or female subjects (aged 18 or over), with non-diseased eyes, who require optical correction for refractive ametropia. The aim is to enroll approximately 812 subjects in approximately 45 US sites, with approximately 18-20 subjects per site. Estimated time needed to recruit subjects for the study is approximately 16 weeks. Competitive enrollment may be implemented across investigative sites should the need arise to help meet the target enrollment objective.

The intended study population consists of volunteer subjects who are frequent replacement daily wear or extended wear soft contact lens wearers, who have at least 3 months of contact lens wearing experience, and who wear their habitual lenses at least 5 days per week. Subjects must have regularly worn their habitual lenses for at least **10 hours** per day. Additionally, extended wear lens wearers must have regularly worn their habitual lenses for at least one night per week. [REDACTED]

[REDACTED]

[figure not shown]
[REDACTED]

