12 ANALYSIS PLAN

Any deviations to the analysis plan will be updated during the course of the study as part of a protocol amendment or will be detailed in the clinical study report.

All analyses will be conducted according to the applicable statistical analysis plan.

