12.6.1.2 Analysis Methods

A generalized linear model, with a logit link function, accounting for within-subject correlation will be fit. A one-sided 95% upper confidence limit (UCL) will be calculated for the difference in proportions between treatments ([REDACTED] contact lens minus Biofinity contact lens), and the null hypothesis will be rejected if $UCL < 0.05$.

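### SAP 5.3.1 puts Site and Site-by-Treatment into the primary logit model; the planned events cannot support them, so the noninferiority verdict depends on an unstated computation

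*SAP*

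**What the plan says.** Protocol 12.6.1.2 describes the primary safety analysis in this way: "A generalized linear model, with a logit link function, accounting for within-subject correlation will be fit". It names no site terms. A one-sided 95% upper confidence limit (UCL) for the difference in proportions is compared with 0.05.

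SAP 5.3.1 repeats that model and adds: "Site and Site-by-Treatment interaction terms will also be included to assess potential effect of sites on treatment difference". The next sentence carries the decision rule. The UCL "will be calculated for the difference in proportions between treatments (Mercury minus Biofinity), and the null hypothesis will be rejected if" it falls below 0.05. The section describes one model and one limit.

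Protocol 12 makes the SAP govern: "All analyses will be conducted according to the applicable statistical analysis plan". The SAP's Executive Summary rests the trial on this test: "Success of this study will be based on demonstration of noninferiority in proportion of ocular serious and significant non-serious adverse device effects".

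The visible text of SAP 5.3.1 does not say:
- whether site is fixed or random;
- how a difference in proportions is obtained from the logit scale;
- how sites are weighted, or whether small ones are pooled;
- what happens if estimates diverge.

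**The concern.** A logit model with fixed Site and Site-by-Treatment terms fits a separate event probability in every site-by-arm cell. A cell with no event has a fitted logit of minus infinity. The event is rare and the sites are small, so most or many cells would be empty and the model would have no finite maximum-likelihood fit.

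Software may still return numbers. What they say about the difference in proportions then depends on where the iterations stop, how sites are averaged and which standard error is used. The SAP fixes none of these. The only confirmatory test in the trial could therefore pass or fail on a programming choice. If the analysts noticed the problem, they would be choosing a replacement model after seeing the event data.

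**Working it through.** **Inputs.** Event rate 0.045, 213 per group, margin 0.05, 284 per arm randomized (Protocol 12.8, SAP 7). Binary outcome per eye (SAP 5.1). Protocol 8 gives the site figures: "The aim is to enroll approximately 812 subjects in approximately 45 US sites, with approximately 18-20 subjects per site". The site count for the primary cohort is blacked out. Its 632 enrolled subjects at 18-20 per site would be 632/20 = 31.6 to 632/18 = 35.1 sites, so I use 32 to 45. Assumptions: fixed site terms, equal site sizes, 0.045 read per eye, and fellow-eye correlation (ICC) of 0, 0.5 or 1.

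**1. The plan's own figure.** n = (1.645 + 0.842)² × 2 × 0.045 × 0.955 / 0.05² = 212.6, so 213; and 213/0.75 = 284. Both reproduce. The formula contains no site terms and treats each subject as one observation.

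**2. Events against parameters.** Expected event eyes are 426 × 2 × 0.045 = 38 (completers) to 568 × 2 × 0.045 = 51 (randomized). The SAP model has 64 cell parameters with 32 sites and 90 with 45.

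**3. Expected empty cells.** The chance that a subject has no event is q = 1 − 2p + p² + ICC × p(1 − p). With p = 0.045 this is 0.9120, 0.9335 and 0.9550 at ICC 0, 0.5 and 1. With S sites and m subjects per cell, the expected number of empty cells is 2S × q^m.

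| Sites | Per arm | m | Cells | ICC 0 | ICC 0.5 | ICC 1 |
|---|---|---|---|---|---|---|
| 32 | 284 | 8.9 | 64 | 28 | 35 | 43 |
| 32 | 213 | 6.7 | 64 | 35 | 40 | 47 |
| 45 | 284 | 6.3 | 90 | 50 | 58 | 67 |
| 45 | 213 | 4.7 | 90 | 58 | 65 | 72 |

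Simulation covered 18 settings (32, 35 and 45 sites; both sizes; three ICCs) with 4,000 trials each, 72,000 in all. No trial had an event in every cell, and the fewest empty cells was 14. Unequal site sizes (coefficient of variation 0.5) raised the means slightly, for example from 64.9 to 65.8 of 90. With only 20 sites, 568 subjects and ICC 0.5, 15 of 40 cells were still empty on average.

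**4. Cell size needed.** For a 95% chance of no empty cell, m = ln(1 − 0.95^(1/(2S))) / ln q. This is about 77 (32 sites, ICC 0) to 162 (45 sites, ICC 1) subjects per site and arm. The plan has about 5 to 9.

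**5. Effect on the decision.** The true rates are 0.095 and 0.045, a difference equal to the margin. The rule is difference + 1.645 × SE < 0.05, with empty-cell logits stopped at −20. There were 10,000 trials per setting except where noted.

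| Route to the UCL | Noninferiority declared |
|---|---|
| Treatment only (protocol model) | 5.2-5.8% |
| SAP model, standardised over the site mix | 6.1-8.2% |
| SAP model, site-averaged least-squares means, robust SE | 97.5-100% |
| Same means, model-based SE (ICC 0.5, 4,000 trials) | 1.5%, 17.0%, 22.3%, 69.7% |

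The last row is in the order 32/284, 32/213, 45/284, 45/213 (sites/per arm). At a true difference of 0.10 and ICC 0.5, robust least-squares means still passed in 80-100% of trials; treatment-only passed in at most 0.02%. Moving the stop to −10, −15 or −28 left the robust route at 95.9-100% (difference 0.05, ICC 0.5).

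The mechanism is simple. With 58.4 of 90 cells empty, the averaged logit is pulled down by about (58.4/90) × (−20) = −13, and exp(−13) is about 0.000002. Both arms appear almost free of events, and empty cells add almost nothing to the robust variance.

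**6. Actual fits.** GEE fits of the SAP model (independence working correlation, robust covariance, ICC 0.5, 60 trials in each of four settings) passed in 239 of 240 trials at a difference of 0.05 and 238 of 240 at 0.10. Treatment-only on the same trials passed in 14 and 0. In one trial the UCL could not be computed. A separate run of 160 such fits reported convergence in all 160, so the failure need not announce itself. With site as main effects only, least-squares means passed in 80 of 80 fits at 0.05, so dropping the interaction alone does not cure it.

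**The case against.** **The alarming route misses the target.** SAP 5.2 defines the parameters as proportions of eyes, and averaged logits do not estimate those. At true rates of 0.095 and 0.045 (ICC 0.5) the median estimate for the test arm was 0.00002 to 0.0012, and for control below 0.00001. Beside the adverse event tables that would look plainly wrong. The route that matches SAP 5.2, standardising over sites, exceeds the treatment-only error by only about 1 to 3 percentage points. This is fair, and the 97.5-100% is not a forecast. But nothing in the visible SAP selects the better route.

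**Site may be random.** Random terms would shrink rather than diverge. However, a generalized linear model with no random terms named is naturally read as fixed effects. A random-effects version would also need a stated route to the difference.

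**The terms may be a supportive check.** Their stated purpose allows this reading, but the text puts them in the model and takes the limit from it.

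**Site adjustment is legitimate.** The allocation design supports it: "Randomization schedule will be blocked to ensure a balance (1:1) in lens allocation within sites". This stands as a reason to examine site. No true site effect is reported in the simulations, so they do not show how the treatment-only limit behaves under strong site differences.

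**Text is missing.** A pooling rule could sit in redacted parts of the SAP. The paragraph in 5.3.1 is itself unbroken and points to none.

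**The model-based figures depend on the stop.** With 45 sites, 284 per arm and ICC 0.5 they range from 19% to 61% as the stop moves from −25 to −8, and one setting lies below 5%. That supports the point that the result is not determined by the SAP.

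**Conclusion.** The concern holds. As written, SAP 5.3.1 departs from Protocol 12.6.1.2 and specifies a primary model that the planned data cannot estimate: 28 of 64 to 72 of 90 cells are expected to be empty. The probability of wrongly declaring noninferiority at the margin then runs from about 6-8% to about 100%, depending on a computation that the visible SAP does not state.

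The sparsity result rests on fixed site terms and the plan's own rate and sample size; it holds at every site count and ICC examined. Reading 0.045 per subject would lower the eye rate and could not reduce the number of empty cells. The size of the consequence depends on the route chosen, so it is a range. The sample size is not in error, but it was derived for a model without site terms.

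**What to change.** Revise SAP 5.3.1 before unmasking:

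1. State that the decision UCL comes from the Protocol 12.6.1.2 model: treatment only, eyes clustered within subject, robust variance, and the difference between the two arm proportions.
2. Remove both Site and Site-by-Treatment from that model.
3. Examine site consistency separately, with no bearing on the decision: event eyes by site and arm, and the treatment-only difference with each site left out in turn.
4. If a site-adjusted result is wanted, make it a sensitivity analysis, for example with a random site intercept or with sites pooled by a rule fixed before unmasking, and state a fallback.

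The cost is one paragraph. Endpoint, margin, enrolment and the UCL < 0.05 rule are unchanged. At a true difference of 0 the treatment-only model had simulated power of 79.8-99.1% across 213 to 284 per arm and ICC 0 to 1, so the planned 80% is essentially kept.
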